#### **1.1.4. Non-radiographical Axial Spondyloarthritis**

The term non-radiographic axial spondyloarthritis (nrAxSpA) is recently being introduced to identify patients suffering from the early phase of AS, where the standard diagnosis, historically based on the presence of sacroiliitis on X-ray, is impossible due to the absence of radiographic changes.

A study demonstrated that the frequency of radiographic sacroiliitis increases in parallel with disease duration and approximately 60% of patients will require at least 10 or more years of active disease to demonstrate its radiographic features seen in “classical” AS (Sahid-Nahal, Miceli-Richard, & Berthelot, 2000).

Therefore today, patients presenting with a clinical picture of AS but without its radiological hallmark, will be diagnosed with nrAxSpA.

This distinction is important as agents effective in alleviating clinical symptoms and signs of AS could be used much earlier in the course of the disease and therefore may prevent structural damage and complications (Rudwaleit, et al., 2009).

## 1.2. Filgotinib (GS-6034)

### 1.2.1. General Information

JAKs are intracellular cytoplasmic TYKs that transduce cytokine signaling from membrane receptors through STAT to the nucleus of cells. JAK inhibitors block the signaling of various cytokines, growth factors, and hormones, including the pro-inflammatory cytokine IL-6. Four different types of JAKs are known, JAK1, JAK2, JAK3, and TYK2 which interact with different sets of membrane receptors. Inhibition of JAKs is a promising therapeutic option for a range of inflammatory conditions including RA and CD. Filgotinib (GS-6034, formerly known as GLPG0634) is a potent and selective inhibitor of JAK1. The compound has shown good preliminary efficacy in subjects with RA and those with CD in Phase 2 studies.

For further information on filgotinib, refer to the current Investigator's Brochure (IB).

### 1.2.2. Preclinical Pharmacology and Toxicology

Filgotinib and its metabolite, GS-829845, have been extensively characterized in nonclinical studies. This program includes cellular assays demonstrating potency and selectivity of the compound against JAK1; efficacy studies in rats and mice; repeat dose toxicity studies (up to 26 weeks in the rat and 39 weeks in the dog), in vitro and in vivo safety pharmacology and genetic toxicology studies, carcinogenicity studies in rats and in transgenic (TgrasH2) mice, and reproductive toxicology studies in rats and rabbits. Additional toxicology studies conducted include phototoxicity studies and dose-range finding studies in support of a definitive rat juvenile toxicity study. A definitive juvenile toxicology study in rats is ongoing.

#### 1.2.2.1. Nonclinical Pharmacology

In cellular assays, filgotinib inhibits JAK1 signaling with half maximum inhibitory concentration ( $IC_{50}$ ) values of  $\geq 179$  nM, and demonstrates 30-fold selectivity over JAK2 in a human whole blood assay. Filgotinib has been profiled against 451 kinases and it is highly selective for JAK1; only 2.5% of kinases were inhibited  $\geq 50\%$  at 50-fold higher concentration than  $IC_{50}$  for JAK1.

#### 1.2.2.2. Safety Pharmacology

Filgotinib and GS-829845 had no relevant effects on cardiovascular parameters (human ether-a-go-go [hERG] and dog telemetry studies), apart from a slight non-adverse increase in heart rate and arterial pressure with GS-829845 at exposures 8-fold that of the peak serum concentration ( $C_{max}$ ) in subjects with CD treated with 200 mg once daily filgotinib. There were no relevant effects on electrocardiogram (ECG) and QT. Filgotinib and GS-829845 had no effects on the respiratory system and central nervous system (CNS).

### **1.2.2.3. Key Nonclinical Distribution, Metabolism, and Excretion Data**

Filgotinib demonstrates good oral bioavailability in mice, rats, dogs, and mini-pigs but less in monkeys. Plasma protein binding is low (<70%) in all species, including humans.

The pharmacokinetics (PK) of filgotinib is generally dose proportional without gender differences. No accumulation occurs with repeated dosing. The mean terminal half-life after oral administration is 4 hours and 5 hours in rats and dogs, respectively.

In the rat, filgotinib showed a rapid and even distribution throughout the body. High concentrations were observed only in the gastrointestinal (GI) tract and urinary bladder. Filgotinib does not penetrate into CNS tissues. The distribution of filgotinib indicates some affinity for melanin-containing tissues.

Excretion is nearly complete within 24 hours (rat) and 48 hours (dog) post-dosing. In the rat, fecal and urinary excretion accounted for 40% and 53% of the administered dose, respectively, with a bile secretion of about 15%. In the dog, fecal excretion was the primary route of excretion, accounting for 59% of the administered dose, with urinary excretion accounting for 25%.

In vitro metabolism studies in all species revealed one major metabolite (GS-829845). The formation of GS-829845 is mediated by carboxylesterases (CES) and is not dependent on cytochrome P450 (CYP).

In vitro experiments have shown that drug-drug interactions with filgotinib and GS-829845 are unlikely. There is no inhibition or induction of CYPs or uridine 5'-diphospho-glucuronosyltransferase (UGTs), and no relevant inhibition of key drug transporters, including organic anion transporters (OATs), by filgotinib or GS-829845. Organic cation transporter 2 (OCT2) was inhibited by both filgotinib ( $IC_{50}$ : 8.7  $\mu$ M) and GS-829845 ( $IC_{50}$ : 67  $\mu$ M). The clinical relevance of the  $IC_{50}$  values for inhibition of OCT2 will be further evaluated. Multidrug and toxin extrusion protein 1 (MATE1) was also weakly inhibited by filgotinib ( $IC_{50}$ : 94  $\mu$ M) and GS-829845 ( $IC_{50}$ : >100  $\mu$ M). Filgotinib was found to be a substrate of P-glycoprotein (P-gp).

### **1.2.2.4. Nonclinical Toxicology**

In repeat oral dose toxicity studies in both rats and dogs, the primary target tissues identified for filgotinib were the lymphoid tissues which are expected based on the pharmacology of JAK inhibition. Additional filgotinib-related findings were observed in the male reproductive organs of both species, and in the incisor teeth of rats only. Effects on the lymphoid system were fully reversible. Testicular toxicity demonstrated partial reversibility; however, sperm counts remained low. When using the mean exposure (area under the plasma drug concentration-time curve [AUC]) at the no observed adverse effect levels (NOAELs) for the most sensitive species (the dog), the exposure margins compared to a 200 mg once daily dose of filgotinib in CD subjects are 2.5, 1.9, and 3.6-fold for the 26-week and 39-week chronic toxicity studies and the 39-week targeted exposure toxicity study, respectively.

GS-829845-related findings in general in the repeat-dose toxicity studies were generally similar to those of the parent filgotinib, however no testicular toxicity was noted following administration of GS-829845.

Filgotinib and GS-829845 were non-genotoxic when evaluated in the bacterial mutagenicity assay, the in vitro mouse lymphoma mutagenicity assay, and the rat bone marrow micronucleus assay.

In embryofetal development studies, filgotinib and GS-829845 caused embryoletality and teratogenicity in rats and rabbits. Teratogenicity was observed at exposures slightly higher or similar to the human exposure at 200 mg once daily of filgotinib in subjects with RA. Administration of filgotinib did not affect female fertility but impaired fertility was observed in male rats at exposures approximately 12-fold the human exposure at 200 mg of filgotinib in subjects with CD. GS-829845 did not have any effects on fertility parameters in either male or female rats.

In an in vitro phototoxicity study in 3T3 cells, the metabolite GS-829845 was positive for phototoxic potential and results with filgotinib were equivocal. A follow-up in vivo rat phototoxicity assay revealed a lack of phototoxic potential for both compounds.

### **1.2.3. Clinical Studies of Filgotinib**

An overview of exposure and clinical studies conducted with filgotinib is available in the IB.

In two 24-week, Phase 2b, randomized, double-blind, placebo-controlled studies in 594 (Study GLPG0634-CL-203) and 283 subjects (Study GLPG0634-CL-204) with moderately to severely active RA who had insufficient response to MTX, filgotinib added to a stable dose of background MTX or administered as monotherapy was efficacious in a dose-dependent manner in treating the signs and symptoms of active RA (Westhovens, et al., 2016; Kavanaugh, et al., 2017). In Study GLPG0634-CL-203, an American College of Rheumatology 20 (ACR20) response was achieved by a statistically significantly higher percentage of subjects in the 100-mg once daily, 200-mg once-daily, and 100-mg filgotinib twice daily groups (63.5%, 68.6%, and 78.6%, respectively) compared with placebo (44.2%) ( $p = 0.0435$ ,  $0.0068$ , and  $<0.0001$ , respectively). In Study GLPG0634-CL-204, an ACR20 response at Week 12 was achieved by a statistically significantly higher percentage of subjects in all filgotinib dose groups compared with placebo (66.7%, 65.7%, and 72.5% in the 50-mg once-daily, 100-mg once-daily, and 200-mg filgotinib once-daily groups, respectively, compared with 29.2% on placebo) ( $p < 0.0001$  for all comparisons). In both studies, the ACR20 appeared to plateau at Week 8 and was maintained through Week 24. In addition, at Week 12, filgotinib showed a beneficial effect across the following secondary efficacy parameters: ACR50, ACR70, ACR-N, Disease Activity Score 28 joints (DAS28) (C-reactive protein [CRP]), Clinical Disease Activity Index (CDAI), and Simplified Disease Activity Index (SDAI). A dose-dependent fast onset of efficacy was reported, and the responses were maintained or continued to improve through 24 weeks. No significant difference in efficacy was observed between 100-mg and 200-mg once daily dosing regimens.

Safety in the proof of concept studies in PsA and AS was in line with the safety profile reported from previous studies with filgotinib in RA and no unexpected safety signals were identified.

### 1.3. Rationale for this Study and Proposed Study Population

Over the last decade, changes in treatment strategies for rheumatic diseases, accompanied by advances in drug development and the addition of targeted biological therapies, have greatly improved the outcomes for patients. Despite these developments, therapeutic challenges remain. Only a subset of patients responds to currently available biologic therapy while others lose response over time or become intolerant over time. There is an unmet medical need for simple, orally administered therapies with novel and targeted mechanisms of action that can effectively improve the disease course while being safe and well tolerated. Filgotinib is an orally administered, small molecule inhibitor of JAK1, an intracellular tyrosine kinase dysregulated in subjects with inflammatory disorders including RA, PsA, AS and nrAxSpA. Filgotinib has demonstrated a favorable safety and tolerability profile in a Phase 2 study in subjects with moderately to severely active RA. Filgotinib is presently being evaluated in Phase 3 studies in CD, ulcerative colitis (UC), and RA. Filgotinib is also being evaluated in, Sjögren's syndrome, cutaneous lupus erythematosus, noninfectious uveitis and lupus membranous nephritis.

While providing a treatment option for subjects with RA, PsA, AS and nrAxSpA, the present study seeks to evaluate the impact, if any, of filgotinib on spermatogenesis in humans. The observed effects of filgotinib on the testes are consistent across the nonclinical species tested, with observations of histopathological changes in testes and epididymides, together with reductions in sperm counts and reduced fertility in the rat. A mechanistic study in the rat suggested a reversible direct impact on the genes involved in cell cycle. A dose of 200 mg once daily of filgotinib results in an estimated mean clinical AUC of 2.8 µg·h/mL in subjects with RA, which represents an exposure margin of 2.3, 1.8, and 3.4-fold when considering the mean AUC in male dogs at the no observed effect levels (NOELs) in the 26-week and 39-week chronic toxicity studies, and 39-week targeted exposure toxicity study, respectively. The present study seeks to assess the impact of filgotinib at 200 mg, the highest proposed dose in the Phase 3 program, assessed by the proportion of male subjects who experience a ≥50% decrease in sperm concentration from Baseline when compared with placebo after 13 weeks of therapy. The proposed study design and subject population for GLPG0634-CL-227 have been selected to generate clinical safety data which would be broadly applicable to patient populations treated with filgotinib.

The present study has been designed in accordance with FDA Guidance for Industry: Testicular Toxicity: Evaluation During Drug Development (October 2018).

The study population will consist of males with active RA (defined as a CDAI score >10), active PsA (defined as DAPSA score >14) or active AS or nrAxSpA (defined as Bath Ankylosing Spondylitis Disease Activity [BASDAI] ≥4). Subjects must have demonstrated a prior treatment failure/intolerance to disease specific therapies but will be allowed to remain on permitted therapy, with the exception of SSZ which will be prohibited due to known risks of oligospermia and infertility {Pharmacia & Upjohn Co 2014}. Subjects will be stratified by Baseline sperm concentration and type of underlying rheumatic disease (RA or spondyloarthritis). In addition, subjects will also be stratified by use of MTX (yes or no) given its potential impact on

spermatogenesis. There have been case reports of reversible oligospermia and azoospermia with treatment with MTX {Sussman 1980}, though a small case series in 26 men with psoriasis aged 33 to 52 treated with MTX at a dose of 25 mg weekly did not reveal any impact of MTX on mean sperm count motility and morphology {El-Beheiry 1979}.

Subjects with mildly decreased testosterone will also be included in the study. The incidence of low testosterone increases with increasing age. The crude incidence of androgen deficiency in 1 large cohort (the Massachusetts Male Aging Study) was 12.3% overall, but increased with increasing age: 5.9% at 40 to 49 years, 11.2% at 50 to 59 years, and 23.3% at 60 to 70 years {Araujo 2004}. One cohort demonstrated a prevalence of hypogonadism in men aged 45 and older (based on total testosterone <300 ng/dL) of 38.7% {Mulligan 2006}. The present study will include men with testosterone levels at or above 80% of normal, given the expected incidence of hypogonadism in the upper age range of the study population.

### **1.3.1. Rationale for the Outcome Measures**

While no single sperm parameter can predict fertility potential, sperm concentration may be considered the most reliably quantifiable parameter that has potential utility in providing information about male fertility (FDA Guidance on Testicular Toxicity, October 2018). Sperm concentration may also be considered the most important parameter of testicular dysfunction (Sikka & Hellstrom, Current updates on laboratory techniques for the diagnosis of male reproductive failure., 2016). The present study will evaluate the reduction in sperm concentration of  $\geq 50\%$  or more from Baseline at 13 weeks as the primary endpoint in accordance with the FDA guidance. Significant variations in sperm parameters are expected in men; a threshold of a  $\geq 50\%$  reduction is considered the appropriate threshold to account for normal variability and is consistent with prior studies evaluating impact of potential testicular toxins (Sikka, et al., 2014; Hellstrom, et al., 2008; Hellstrom, et al., 2003; Jarvi, et al., 2008). Substantial intra- and inter-subject variation can occur particularly in sperm count in patients with and without fertility issues; in one cohort, sperm counts ranged over an order of magnitude in a single healthy patient over time (Keel, 2006). Two semen samples will be collected for evaluation at each time point during this study, with controlled abstinence periods before each sample collection; longer or shorter abstinence periods may have an impact on quality of sample. Ejaculate volume and sperm count are markedly reduced during periods of high ejaculation frequency (Oldereid, Gordeladze, Kirkhus, & Purvis, 1984). Significant variability is noted even in healthy subjects (World Health Organization (WHO), Laboratory Manual for the examination of human semen and sperm-cervical mucus interaction. Fourth Edition., 1999; World Health Organization (WHO), Laboratory manual for the Examination and processing of human semen. Fifth Edition., 2010). Additional sperm parameters at 13 weeks will be evaluated as secondary endpoints in alignment with the FDA Guidance on Testicular Toxicity (October 2018).

The primary endpoint at Week 13 will enable a direct assessment versus placebo in subjects with RA, PsA, AS, and nrAxSpA. Endpoints at 26 weeks of therapy have been chosen for secondary and exploratory analyses to assess impact after 2 full spermatogenesis cycles in accordance with The FDA Guidance on Testicular Toxicity (October 2018), which recommends treatment for 26 weeks for drugs that are chronically dosed. The 26-week endpoint will also allow assessment of the impact of longer-term therapy on semen parameters, given the expectation for chronic dosing of therapy in the real world setting. Finally, in the present study, total motility, which is

considered to be more consistently measured across observers, will remain as a secondary endpoint.

In this study the ACR/EULAR (2010) criteria will be used to define a diagnosis of RA, the CASPAR criteria will be used to define a diagnosis of PsA, and the Assessment of Spondyloarthritis International Society (ASAS) criteria for will be used to define a diagnosis of axial spondyloarthritis (AS or non-radiographical axial spondyloarthritis [nrAxSpA]) for the purpose of eligibility.

Subjects with RA and PsA will be required to have an inadequate response or intolerance to at least a 12-week course of csDMARD or biological DMARD (bDMARD) therapy for their arthritis. Subjects with AS and nrAxSpA will be required to have an inadequate response or intolerant to at least 2 NSAIDs (see Section 4.2).

At the Week 13 Visit, Physician Global Assessment of Disease Activity (PhGADA) will be used to determine arthritis Responder, and arthritis Non-responder status. During the Extension Phase, individual subject response to treatment has to be evaluated at each visit in accordance with good rheumatology practice.

This study is based upon real world outpatient clinical practice, where clinical signs/symptoms (and labs as applicable) and a provider's assessment are adequate to assess therapeutic response or non-response. Safety and tolerability will be assessed by the evaluation of adverse events (AEs), selected clinical laboratory parameters, vital signs, physical examinations, and ECGs all of which are standard safety evaluations in clinical development. All subjects who experience a  $\geq 50\%$  decrease in sperm concentration and/or total motility and/or normal morphology will be followed for one or more spermatogenesis cycles, up to 52 weeks as needed, to assess for sperm parameter reversibility.

### **1.3.2. Rationale for the Choice of Dose and Dosing Interval**

The 200 mg once daily dose level of filgotinib is currently the highest clinical dose being evaluated in Phase 3 studies of RA, UC, and CD.

### **1.4. Risk/Benefit Assessment for the Study**

Over the last decade, changes in RA and PsA treatment strategies, accompanied by advances in drug development and the addition of targeted therapies, have improved patient outcomes. Despite these developments, therapeutic challenges remain. Current csDMARDs and bDMARDs may produce only partial responses in some patients and may be associated with significant safety and tolerability concerns. There is an ongoing need for orally administered therapies with novel and targeted mechanisms of action that can more effectively improve the disease course.

Nonclinical studies in rats and dogs identified lymphoid tissues and testes as target organs for filgotinib in long-term repeat-dose toxicity studies. Although decreased lymphocyte numbers observed in nonclinical studies have not been seen in clinical studies, hematological assessment will be performed throughout the present study to ensure this potential risk is appropriately monitored. In both rats and dogs, microscopic findings in the testes included germ cell depletion and degeneration, with reduced sperm content and increased cell debris in the epididymis and

reduction in fertility in male rats. The dog was determined to be the most sensitive species. When using the AUC at the NOAELs for dogs in the 26-week and 39-week chronic toxicity studies, and the 39-week targeted exposure toxicity study, the exposure margins compared with the highest proposed clinical dose of 200 mg once daily are 2.5, 1.9, and 3.6-fold respectively, in subjects with RA. To assess this potential risk to male fertility, the male safety clinical study described herein is planned to examine the effect of filgotinib (if any) on sperm/ejaculate parameters. Male subjects who enroll will be appropriately consented via the informed consent form (ICF) wherein risk language is highlighted. Impaired spermatogenesis is considered to be a potential risk for filgotinib. Refer to the IB for further information about nonclinical and clinical testicular findings.

Filgotinib has shown an increased risk in embryofetal malformations in rats and rabbits at exposures similar to, or slightly higher than, exposures associated with a 200 mg once daily dose in subjects with RA. As a result, highly effective contraception and male condoms will be required for male subjects with female partners of childbearing potential, which is expected to mitigate this risk.

JAK inhibition is expected to increase the risk of infection based on mechanism of action. Across the global studies in filgotinib, in general, active treatment arms have increased incidences of infection versus placebo. In the present protocol, treatment interruption and discontinuation considerations surrounding infections are incorporated, and sites and investigators will be trained regarding such circumstances. All subjects will be screened for TB, and subjects with active infections will be excluded. Malignancy has been reported in subjects on filgotinib; in the present study, subjects with recent malignancies will be excluded as outlined in the inclusion criteria. For further details about infections and malignancies, please reference the IB.

The potential benefits of JAK inhibition include improvement in clinical symptoms. JAK inhibition may be efficacious in the treatment of RA, PsA, AS and nrAxSpA based on results from the Phase 2 studies of subjects with PsA, and AS. Filgotinib is currently in Phase 3 studies for RA.

Overall, clinical findings and laboratory changes associated with filgotinib are consistent with JAK 1 inhibition. Based on Phase 2 and Phase 3 data the expected benefit of using filgotinib as proposed in this study is considered to outweigh any associated risks. In addition, the subject population in the present study will consent to a risk of potentially permanent infertility, thus individual male subjects in conjunction with the treating physician may evaluate the benefit-risk profile of filgotinib. A lack of response contingency from Week 13 onward in the current study, targeting arthritis Non-responders at Week 13, will enable early access to active drug or Standard of Care treatment when clinically indicated. This rescue approach, the provision of best supportive care during the extension phase, and the limited study duration, makes the use of placebo ethically acceptable for the specified duration.

An external multidisciplinary Data Monitoring Committee (DMC), including an expert in male fertility, will be appointed to monitor the study.

The DMC has monitored the study until the date of protocol amendment 2, including the data for the second unblinded interim analysis (IA2). As of amendment 2, the DMC will be

decommissioned. Details on the DMC's role have been described in a specific charter. The DMC's role will be transferred to the internal Sponsor Safety Management Team (SSMT). The SSMT is not involved in the conduct of the study and will evaluate safety data throughout the remainder of the study as part of continuous safety oversight across the filgotinib program.

Taking all of these considerations into account with respect to the filgotinib program, the early signals for efficacy demonstrated in Phase 2 and Phase 3 clinical studies of RA, AS and PsA, as well as the beneficial findings in nonclinical models of disease and the overall safety, tolerability, and PK characteristics of filgotinib elucidated to date, there is a favorable benefit-risk profile for this agent in continued development as a treatment for RA, PsA, AS, and nrAxSpA. The overall benefit-risk balance of this study is considered favorable.

For additional information about the risks of filgotinib, reference the latest version of the filgotinib IB.

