6) If using csDMARD therapy, subjects are permitted to use one of the following drugs, alone or in combination (with the exception of the MTX-LEF combination) and must have been on a stable dose of the drug for at least 4 weeks prior to Screening and remain on a stable dose during the Double-blind Treatment Phase of the study (stable dose in all cases is defined as no change in prescription):

- a) MTX oral or parenteral up to 25 mg/week (plus concomitant use of folic or folinic acid supplementation as per local Standard of Care)
- b) Leflunomide (LEF) up to 20 mg/day orally
- c) Hydroxychloroquine up to 400 mg/day or chloroquine up to 250 mg/day orally
- d) Apremilast orally up to 30 mg twice daily

Note that SSZ is not permitted at any time, beginning 26 weeks prior to Screening until the end of the study, and cannot be included in the Standard of Care arthritis regimen, due to its potential impact on semen parameters.

- 7) The mean of 2 separate semen samples collected at Screening must meet the following minimum criteria (in accordance with Section 6.11): semen volume  $\geq$ 1.5 mL, total sperm per ejaculate  $\geq$ 39 million, sperm concentration  $\geq$ 15 million per mL, sperm total motility  $\geq$ 40% and normal sperm morphology  $\geq$ 30%
- 8) LH, FSH, inhibin B, and total testosterone values within 20% of laboratory reference ranges during Screening
- 9) Subjects who engage in heterosexual intercourse must agree to use protocol-specified method(s) of contraception as described in [Appendix 10](#) including use of condoms during the study and for 90 days after the last dose of study drug
- 10) Willingness to refrain from receiving live and attenuated vaccines within 30 days of Day 1, throughout the study, and for 12 weeks after the last dose of study drug (Section 5.4, Vaccine Guidelines).
- 11) Meet one of the following 3 TB Screening criteria:
  - a) No evidence of active or latent TB:
    - A negative QuantiFERON® TB-Gold Plus In-Tube test at Screening, AND
    - A chest radiograph (views as per local guidelines) taken at Screening or within the 3 months prior to Screening (with the report or films available for investigator review) without evidence of active or latent TB infection, AND
    - No history of either untreated or inadequately treated latent TB infection
  - b) Previously treated for TB:

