## **Appendix 10. Pregnancy Precautions, Definition for Female of Childbearing Potential, and Contraceptive Requirements**

The administration of filgotinib in embryofetal animal development studies resulted in decreased numbers of viable rat fetuses, increased resorptions, and visceral and skeletal malformations. Similar effects were noted in the rabbit. A safety margin relative to human exposure has not been identified. Pregnancy is contraindicated during use of filgotinib.

For participation in this study, men must agree to use condoms during the study and for 90 days after the last dose of study drug. Female sexual partners of childbearing potential, defined below, should also consider use of highly effective contraception as outlined below.

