### **2) Contraception for Female Sexual Partners of Male Subjects**

#### **1. Study Drug Effects on Pregnancy and Hormonal Contraception**

Filgotinib is contraindicated in pregnancy as there is a possibility of human teratogenicity/fetotoxicity in early pregnancy based on non-clinical data. Data from a drug-drug interaction study of filgotinib and hormonal contraceptives (GS-US-417-3916) have demonstrated co-administration with filgotinib did not alter the pharmacokinetics of representative hormonal contraceptives (levonorgestrel/ethynodiol). For male subjects, male condom should be used; for their female partners of childbearing potential an accepted contraceptive method should also be considered. Details are outlined below.

Please refer to the latest version of the filgotinib IB for additional information.

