## **3) Contraception for Male Subjects**

It is theoretically possible that a relevant concentration of study drug may be achieved in a female partner from exposure to the male subject's seminal fluid. Therefore, male subjects with female partners of childbearing potential must use condoms during study participation and for 90 days after the last study drug dose. Female partners of male study subjects should consider using one of the above methods of contraception as well. Male subjects must also refrain from sperm donation during treatment and until at least 90 days after the last study drug dosing.

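### Protocol Section 1.4 makes highly effective contraception a requirement, but Appendix 10 only asks female partners to consider it

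*Protocol*

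**What the plan says.** Protocol Section 1.4 reports malformations in rats and rabbits at exposures close to those reached at 200 mg once daily. It concludes that "highly effective contraception and male condoms will be required for male subjects with female partners of childbearing potential", and adds of this combination: "which is expected to mitigate this risk".

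Inclusion criterion 9 (Section 4.2) says that subjects who have heterosexual intercourse "must agree to use protocol-specified method(s) of contraception as described in" Appendix 10. It names condoms as included and sets the period as the study plus 90 days after the last dose.

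Appendix 10 opens with the condom rule, "men must agree to use condoms during the study and for 90 days after the last dose of study drug", and follows it with "Female sexual partners of childbearing potential, defined below, should also consider use of highly effective contraception as outlined below". Its part on contraception for female partners says that "for their female partners of childbearing potential an accepted contraceptive method should also be considered". Its part on male subjects repeats the condom obligation and adds: "Female partners of male study subjects should consider using one of the above methods of contraception as well".

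**The concern.** Section 1.4 is where the Protocol explains how each known hazard is controlled. For the embryofetal hazard it names two mandatory measures. The appendix that investigators and subjects follow imposes one of them and leaves the other to the partner's consideration. A reader of Section 1.4, such as an ethics committee, would believe that a safeguard is in force which the working text does not impose.

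The Protocol treats the hazard seriously. Appendix 10 says that no margin relative to human exposure has been established and that pregnancy is contraindicated during use of the drug. It also regards exposure of a female partner through seminal fluid as theoretically possible. With about 150 centres planned (Synopsis), sites could apply the rule differently, some insisting on a listed partner method and others only on the condom.

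**Working it through.** The plan gives no figure to reproduce. The check sets the statements side by side and asks, for each, what is mandatory.

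| Place in the Protocol | Condom | Highly effective or other partner method |
|---|---|---|
| Section 1.4 | Required | Required |
| Section 4.2, criterion 9 | Included among the methods to be used | Left to Appendix 10 |
| Appendix 10, introduction | Mandatory | To be considered |
| Appendix 10, part 2, item 1 | Should be used | To be considered |
| Appendix 10, part 2, item 2 | Mandatory | Recommended; the subject must pass the information on |
| Appendix 10, part 3 | Mandatory | To be considered |

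1. **Tally for the partner method.** One place (Section 1.4) requires it. Four statements in Appendix 10 make it optional: three say it should be considered and one calls it recommended. No statement in Appendix 10 requires it.

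2. **Does the list of methods in Appendix 10 create an obligation?** Part 2, item 2 lists abstinence or one of several methods used consistently and correctly. The list is introduced as information on recommended methods that the subject must share. The note tying hormonal methods to condom use is a condition on those methods once chosen. It does not oblige anyone to choose one.

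3. **Does criterion 9 resolve the conflict?** It says *must*, allows for more than one method, and names condoms as included. It takes its content from Appendix 10, so it can be read as requiring a listed method or as requiring what the appendix makes mandatory, which is the condom. It leaves the question open.

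4. **Is there an innocent explanation in the text?** The summaries of changes for Amendments 1 and 2 list no change to the contraception rules, and nothing is blacked out in these sentences. All of them are current text.

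5. **Who is affected, and for how long?** Subjects are randomized 1:1, and those on placebo move to Standard of Care or the Monitoring Phase without receiving filgotinib, so the drug-related risk concerns the filgotinib arm. Sections 3.6 and 4.2 give the longest relevant period, for a subject who stays on open-label filgotinib to the end: 13 + 143 = 156 weeks; 156 × 7 = 1,092 days; 1,092 + 90 = 1,182 days from first dose. The documents do not say how many subjects have partners of childbearing potential, nor give any pregnancy rate.

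**The case against.** The strongest reply is that the gap is narrow. The condom is mandatory throughout, and Appendix 10 ties it directly to the seminal-fluid route. Other safeguards are also imposed: sharing contraceptive information with the partner, no sperm donation until at least 90 days after dosing, a list of unacceptable methods, and prompt reporting of partner pregnancies (Section 7.7.2.1). This stands. A reader might infer that the mitigation described in Section 1.4 is absent from the working rules. The documents do not support that, because only the additional highly effective method is in dispute.

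A reader might also infer that the favourable risk/benefit conclusion falls with this sentence. It does not. The concluding paragraphs of Section 1.4 cite Phase 2 and Phase 3 data, nonclinical findings, and overall safety, tolerability and pharmacokinetics. They do not name contraception.

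A third reply is that a trial cannot bind partners who are not its subjects. That may explain the wording of the appendix, but Section 1.4 would then describe a requirement that is not imposed, and the conflict remains.

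Finally, Amendment 2 says the study has passed the time points of its primary, secondary and exploratory endpoints, so rewording criterion 9 would have little effect on who is enrolled. That limits the practical reach. The same amendment describes the study as ongoing, so subjects may still be on open-label filgotinib or within 90 days of their last dose.

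**Conclusion.** The Protocol contradicts itself on a patient-safety rule. Section 1.4 requires highly effective contraception as well as condoms and relies on the pair as mitigation, while Appendix 10 requires only the condom. Criterion 9 does not say which applies, so it would go too far to call it a condom-only rule.

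The size is one disputed measure, relevant to filgotinib-exposed subjects with partners of childbearing potential, during the study and for 90 days after the last dose. No pregnancy risk can be attached to it from these documents. No endpoint, estimate or analysis changes.

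The conclusion rests on reading *should consider* and *recommended* as not mandatory. It assumes nothing about the consent form, whose pages are not available for review, so it cannot be said that subjects were misinformed.

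**What to change.** Reconcile Section 1.4, inclusion criterion 9 and all parts of Appendix 10 so that one requirement is stated throughout, and make Section 1.4 describe the measure actually imposed. Criterion 9 should say plainly whether agreeing to the specified methods means the condom alone or the condom with a listed partner method. Check the consent form against the reconciled text and change it only if it differs. Which requirement is right is the sponsor's clinical decision and is not proposed here.

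The change is to Protocol wording, with an amendment and any consent update that the check shows to be needed. It requires no new data and no change to the SAP.
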